6.2.2 Maximum administered dose / maximum tolerated dose

The MAD is defined as the highest dose intensity at which at least 2 out of 3 or 2 out of 6 patients experienced DLTs during the initial DLT observation period (Cycle 1). The MTD is defined as the highest dose intensity at which 0 out of 3 or no more than 1 out of 6 patients experienced DLT.

6.3 PART 2

Phase 2 will have 3 arms (if the MTD or RP2D is at DL1 or DL-1) or 2 arms (if the MTD or RP2D is at DL-2) to assess the treatment response and safety of the combination therapy compared with isatuximab alone. After confirmation of eligibility criteria, patients will be randomly assigned using an interactive response technology (IRT), in a 1:1:1 ratio or 1:1 ratio in 1 of the 3- or 2-arm, respectively, with 35 patients in each arm.

If RP2D is DL1:

- Arm 1 (control): isatuximab 10 mg/kg QWx4 followed by Q2W.
- Arm 2 (DL1): isatuximab 10 mg/kg QWx4 followed by Q2W + cemiplimab 250 mg Q2W.

- Arm 3 (DL-1): isatuximab 10 mg/kg QWx4 followed by Q2W + cemiplimab 250 mg Q4W.

If RP2D is DL-1:

- Arm 1 (control): isatuximab 10 mg/kg QWx4 followed by Q2W.
- Arm 2 (DL-1): isatuximab 10 mg/kg QWx4 followed by Q2W + cemiplimab 250 mg Q4W.
- Arm 3 (DL-2): isatuximab 10 mg/kg Q2W + cemiplimab 250 mg Q4W.

If RP2D is DL-2:

- Arm 1 (control): isatuximab 10 mg/kg QWx4 followed by Q2W.
- Arm 2 (DL-2): isatuximab 10 mg/kg Q2W + cemiplimab 250 mg Q4W.

6.3.1 Anti-CD38 refractory cohort

Patients who received anti-CD38 mAb within 6 months before study entry and had disease progression while on treatment or within 60 days after the last treatment will be enrolled in a separate cohort. A decision will be made to start the cohort after the planned Phase 2 interim analysis suggested a treatment benefit of the combination therapy including pass the futility check. The dose and schedule will be determined based on the efficacy and safety findings in the interim analysis

6.4 RETREATMENT OF PATIENTS

Study treatment can continue until disease progression, unacceptable adverse reactions, or patient/investigator decision to continue.

A cycle is 28 days, and deemed to have been delayed if the treatment is >3 days beyond the theoretical day of treatment. The reason for dose delay will be provided.

In the event of toxicity, in order for patients to be retreated, see [Section 6.5](#) and [Appendix G](#) for retreatment recommendations.

6.5 DOSE DELAYS/ MODIFICATIONS

6.5.1 General rules

Dose modifications are permitted according to the guidelines described in this section.

Dose modifications different from those stated in the protocol should only be made in consultation with the Sponsor unless required for immediate patient safety.

Dose adjustment and/or cycle delay are permitted in case of toxicity. Dose adjustments will be made according to the worst grade of toxicity observed within a cycle. If a patient experiences several toxicities and there are conflicting recommendations, the most conservative dose adjustment recommended should be followed. Once a dose has been decreased, intra-patient re-escalation back to the previous dose level is not permitted.

Administration of the study treatment will be discontinued in the event of a TEAE that persists despite appropriate dose modifications or any other AE that, in the opinion of the Investigator, warrants discontinuation.

If one of the 2 drugs (cemiplimab or isatuximab) is prematurely permanently discontinued, the other drug can be continued until disease progression, unacceptable adverse reaction, patient's refusal of further treatment, or in the absence of a clear benefit from therapy. The end of treatment assessment in this case will be 30 days after the date of the last IMP administration.

All changes to study treatment administration must be recorded in the eCRF.

6.5.2 Dose delay and dose omission

Within a cycle, the treatment window is ± 1 day for each of the weekly administrations, ± 2 days for each of the Q2W administrations and ± 4 days for each of the Q4W administrations. A dose is deemed to have been delayed if the treatment is ≥ 2 days beyond the theoretical day of treatment for weekly dose, ≥ 3 days beyond the theoretical day of treatment for Q2W dose and ≥ 5 days beyond the theoretical day of treatment for Q4W dose. The reason for dose delay will be captured. Patient will receive the next infusion after recovery of the toxicity as described in [Section 6.5.3](#) and [Section 6.5.4](#). If infusion has been delayed by 2 days within a cycle, next study treatment should be administered at the planned time interval between 2 administrations (eg, Day 15 Cycle 1 administration is actually administered on Day 17, the planned Day 22 should be administered on Day 24).

Patients may have dose omission if toxicity occurs and does not recover according to following rules:

- In Cycle 1 if toxicity occurs and does not recover on the day of planned infusion or within the following 3 days, infusion of isatuximab and/or cemiplimab may be omitted.
- In Cycle 2 and beyond, if toxicity occurs and does not recover on the day of planned infusion or within the following 7 days, infusion of isatuximab and/or cemiplimab may be omitted for patient on Q2W dose schedule.

In case of consecutive dose omissions for the recovery of toxicity, following rules should be followed for restart or discontinue the treatment:

- Dose interruption (cycle delay) up to 14 days, it is per Investigator's decision to restart the treatment of cemiplimab and isatuximab.
- After dose interruption of >14 days, it is per Investigator's decision to restart the treatment of cemiplimab and isatuximab, if a clear benefit from therapy is observed and after consultation with the sponsor.

- Treatment with isatuximab and cemiplimab must be definitely discontinued if the interruption is longer than 84 days.

6.5.3 Dose modifications

Dose reduction of cemiplimab is permitted for patients treated at the starting dose level and will consist in time interval increase between 2 planned infusions (Table 2).

Table 2 - Dose reduction guidance

Dose level	Isatuximab*		Cemiplimab	
	Dose (mg/kg)	Frequency	Dose (mg)	Frequency
Starting dose	10	QW x4 >Q2W	250 mg	Q2W
Dose reduction	10	QW x4 >Q2W	250 mg	Q4W

* No dose reduction for isatuximab

Guidelines for isatuximab and cemiplimab dose modifications and treatment discontinuation due to hematological and non-hematological adverse reactions in general are outlined in Table 3.

See Section 6.5.4 and Appendix G for guidance for immune-related AEs (irAEs) correlated with cemiplimab, and Section 6.5.5 for infusion associated reactions (IARs) correlated with isatuximab and cemiplimab.

The final decision will be per Investigator's judgment for the best interest of the patient.

Table 3 - Isatuximab and cemiplimab dose modification guidelines

Toxicity NCI CTCAE V4.03	Isatuximab dose management	Cemiplimab Dose management	Action and Guidelines
Hematological toxicity			
Grade 1, 2, 3	No change in dose		Patient should be given supportive care and monitored closely.
Grade 3 thrombocytopenia lasting >7 days or associated with bleeding	Delay the dose until bleeding is controlled and platelet >50 000/mm ³ . Restart treatment with same dose and schedule.		Patient should be given supportive care and monitored closely.
Grade 4	Delay the dose until ANC>1000/mm ³ , Platelet >50 000/mm ³ . Restart with same dose and schedule. Grade 4 lymphopenia: no change in dose		Permanent discontinuation should be considered if toxicity does not resolve within 84 days of last infusion.
Febrile neutropenia and/or neutropenic infection	Delay the dose until fever and infection recover and ANC>1000/mm ³ . Restart with same dose and schedule.		

Toxicity NCI CTCAE V4.03	Isatuximab dose management	Cemiplimab Dose management	Action and Guidelines
Non-hematological toxicity (other than irAE and IAR)			
Grade 1	No Change in Dose	No Change in Dose	N/A
Grade 2	Delay the dose until improves to Grade ≤1 or baseline. Restart treatment at same dose and schedule	Delay the dose until improves to Grade ≤1 or baseline. Restart at same dose and schedule	It is up to the investigator's judgment whether to restart the treatment of isatuximab and cemiplimab if the interruption is within 14 days.
Grade 3	Delay the dose until improves to Grade ≤1 or baseline. Restart at same dose and interval	Delay the dose until improves to Grade ≤1 or baseline. 1 st episode lasts <14 days: restart at same dose 1 st episode lasts >14 days or recurrence: restart with first reduction dose (Q4W administration if began at Q2W starting dose). If began at DL-1, consider discontinuation 2 nd episode lasts >14 days or multiple recurrences discontinue treatment.	If the treatment interruption is longer than 14 days, before restarting the treatment, the investigator must discuss with sponsor; if it is determined that it is to the best interest of the patient, the treatment may be restarted. If the interruption is longer than 84 days, the treatment must be definitely discontinued.
Grade 4	Permanent discontinue treatment for treatment related AEs		
Immune-related AE (irAE): see Table 4 and Appendix G for dose modification and patient management guideline)			
Infusion Associated Reaction (IAR): see Table 5 for IAR management guideline			

6.5.4 General guidelines for the management of immune-related adverse events

Investigators must be extremely vigilant and be ready to intervene early in the management of immune-related AE (irAEs) because the onset of symptoms of irAEs (eg, pneumonitis) may be subtle.

- Detailed guidance for the management of specific irAEs (Colitis, Endocrine AE, Pneumonitis, Renal AE, Dermatologic AE, Hepatitis, Ophthalmologic AE [Uveitis]), plus Nausea and Vomiting is provided in [Section 19](#), [Appendix G](#).
- General guidance is provided in [Table 4](#).
- If a patient experiences several irAEs which involve different recommendations, the most conservative recommendation should be followed.

The recommendations provided in [Table 4](#) and [Appendix G](#) should be seen as guidelines, and the treating physician should exercise clinical judgment based on the symptoms and condition of the individual patient.

Any patient currently receiving cemiplimab who was previously treated with a phosphatidylinositol 3-kinase (PI 3-K) inhibitor and who develops stomatitis or mucositis should temporarily suspend study treatment. If this or any other immune-related AE occurs among these patients, the sponsor should be informed as soon as possible to discuss further management of the patient. An irAE of any grade in a patient previously treated with a PI 3-K inhibitor should be reported as an adverse event of special interest (AESI).

Table 4 - General guidelines for immune related adverse events

Severity	Withhold/Restart /Discontinue isatuximab Treatment	Withhold/Restart/Discontinue cemiplimab Treatment	Supportive Care
Grade 1	No action	No action	Provide symptomatic treatment.
Grade 2	No action	May delay the dose until Grade ≤1	Consider systemic corticosteroids (Prednisone 0.5 to 1 mg/kg/day or equivalent) in addition to appropriate symptomatic treatment.
Grade 3 Grade 4	Delay the dose Restart treatment when Toxicity improves to Grade ≤1 or baseline.	Delay the dose Restart treatment Toxicity improves to Grade ≤1 or baseline Discontinue if unable to reduce corticosteroid dose to <10 mg per day prednisone equivalent within 12 weeks of toxicity.	For any Grade 3-4 immune-related adverse event, if symptoms worsen or do not improve on adequate corticosteroids (Prednisone 1 to 2 mg/kg/day or equivalent) within 48 to 72 hours), consider additional immunosuppressive agents (to be selected from agents such as: infliximab, cyclophosphamide, cyclosporine, and mycophenolate mofetil). Referral of the patient to a specialized unit for assessment and treatment should be considered.

6.5.5 General guidelines for the management of IARs

See [Appendix H](#).

Patients should routinely receive premedications prior to isatuximab infusion as detailed in [Section 8.2](#) to reduce the risk and severity of IARs commonly observed with mAbs.

Infusion associated reactions (which include NCI-CTCAE, version 4.03 terms "allergic/hypersensitivity reactions" and "cytokine release syndrome/acute infusion reaction") typically occurs within 24 hours from the start of the infusion. If an IAR is observed, patients must also be informed of the potential risk of recurrent allergic reactions at subsequent infusions.

Summary of IAR management is provided in [Table 5](#).

Patients who experience Grade 2 IARs may resume cemiplimab/isatuximab infusion after temporary interruption, under close monitoring and with therapy as needed. Patients may receive additional medication per the judgment of the Investigator. Additional recommended medications

are: diphenhydramine 25 mg IV (or equivalent) and methylprednisolone 100 mg IV (or equivalent).

Once a Grade 2 IAR has improved or resolved to Grade ≤ 1 , the infusion may be restarted:

- For cemiplimab, the infusion should be restarted at one half the original infusion rate.
- For isatuximab, the infusion should be restarted at one half the original infusion rate, see [Section 8.4](#) for infusion rate. If symptoms do not recur after 30 minutes, the infusion rate may be increased in 50 mg/hour increments every 30 minutes, to a maximum of 400 mg/hour. Patients with Grade 3 or 4 IAR must have cemiplimab and/or isatuximab permanently discontinued and appropriate therapy should be administered:

If a Grade 3 or high IAR occurred during cemiplimab infusion, cemiplimab should be permanently discontinued. Patient can continue treatment with isatuximab.

If a Grade 3 or high IAR occurred after the start of isatuximab infusion, patient should be permanently discontinued the treatment of both cemiplimab and isatuximab.

Should an IAR of Grade ≥ 2 occur, additional blood sampling during the AE is required for analysis of cytokine levels (TNF- α , IL-6, IL-1- β , and IFN- γ), markers of complement activation (C3a, C4, CH50), serum tryptase, and markers of potential TLS (uric acid, lactate dehydrogenase [LDH], BUN/creatinine, potassium, phosphate, corrected calcium or ionized calcium). The infusion reaction and the therapy administered must be documented in the CRF.

Grade 2 or higher IARs must be reported as AESIs (see [Section 10.5](#)). Study personnel should consult the Medical Monitor for further guidance regarding re-treatment of patients with infusion reactions and regarding issues of premedication management (eg, alternative medications for patients allergic or intolerant to premedication agents) or to determine if locally used equivalent medications are acceptable.

Table 5 - IAR management

Infusion Related Reaction grading (NCI-CTCAE v4.03 criteria)	Recommendation

Mild Grade 1 Infusion interruption or intervention not indicated
	
Continuation of cemiplimab/ isatuximab infusion is per the judgment of the Investigator following close direct monitoring of the patient's clinical status. Cemiplimab/Isatuximab infusion may be stopped at any time if deemed necessary. If stopped, IAR will be classified as Grade 2 as per NCI-CTCAE definition.

Moderate Grade 2 Therapy or infusion interruption indicated but responds promptly to symptomatic treatment (eg, antihistamines, NSAIDS, narcotics, IV fluids); prophylactic medications indicated for ≤ 24 hrs)
	
Stop cemiplimab/isatuximab infusion. Give additional medication(s) with IV diphenhydramine 25 mg IV (or equivalent) and/ or IV methylprednisolone 100 mg (or equivalent) as needed. cemiplimab*/Isatuximab** may be resumed only after patient recovery, with close monitoring.
 
Blood samples for safety labs must be collected at listed as below: Important: additional blood sampling during the AE is required for analysis of cytokine levels (TNF-α, IL-6, IL-1-β, and IFN-γ), markers of complement activation (C3a, C4, CH50), serum tryptase, and markers of potential TLS

Infusion Related Reaction grading (NCI-CTCAE v4.03 criteria)	Recommendation

Severe or Life-threatening Grade 3: Prolonged (eg, not rapidly responsive to symptomatic medication and/or brief interruption of infusion); recurrence of symptoms following initial improvement; hospitalization indicated for clinical sequelae
	
Stop cemiplimab/isatuximab infusion. Give additional medication(s) with diphenhydramine 25 mg IV (or equivalent) and/ or IV methylprednisolone 100 mg (or equivalent) and/or epinephrine as needed. If IAR occurred during cemiplimab infusion, permanently discontinue cemiplimab. Continue treatment with isatuximab. If IAR occurred after the start of isatuximab infusion, permanently discontinue both cemiplimab and isatuximab.


Grade 4: Life-threatening consequences; urgent intervention indicated
	
Blood samples for safety labs must be collected at listed as below: Important: additional blood sampling during the AE is required for analysis of cytokine levels (TNF-α, IL-6, IL-1-β, and IFN-γ), markers of complement activation (C3a, C4, CH50), serum tryptase, and markers of potential TLS

* Cemiplimab: The prepared infusion bag should be kept no more than 8 hours at room temperature between +15°C to +25°C (59°F to 77°F), or no more than 24 hours at 5°C (with an acceptable operating range of 2°C to 8°C refrigerator).

** Isatuximab: the resulting solution for infusion should be used within 16 hours at room temperature between +15°C to +25°C (59°F to 77°F) from the bag preparation to the end of IV infusion of the patient or a new infusion should be prepared with the remaining dose to be administered the same day.

6.5.6 Guidelines for the management of potential tumor lysis syndrome (TLS)

In case of TLS, study treatment should be held until all serum chemistries have resolved. To ensure normal hydration, correct laboratory abnormalities, fluid overload, electrolyte or acid-base deviation. Management must be done according to the local site guideline. Use of xanthine oxidase or urate oxidase is allowed.

TLS complications including renal function should be monitored, and study treatment can be reinstated at full doses after resolution.

Possible clinical and laboratory abnormalities which can be associated with TLS are presented in [Table 6 \(45\)](#).

Table 6 - Laboratory and clinical abnormalities possibly consistent with TLS

Laboratory	Clinical

Uric acid >8 mg/dL (>475.8 μmol/L) Potassium >6.0 mmol/L Phosphorus >4.5 mg/dL (>1.5 mmol/L) Corrected calcium^a <7.0 mg/dL (<1.75 mmol/L) or ionized calcium <1.12 mg/dL (<0.3 mmol/L)
	
 Acute kidney injury: increase in the serum creatinine level of 0.3 mg/dL (26.5 μmol/L) or the presence of oliguria, defined as an average urine output of <0.5 mL/kg/hr for 6 hours Seizures, cardiac dysrhythmia, neuromuscular irritability (tetany, paresthesias, muscle twitching, carpopedal spasm, Trousseau's sign, Chvostek's sign, laryngospasm, bronchospasm), hypotension, or heart failure probably or definitely caused by hypocalcemia Dysrhythmias probably or definitely caused by hyperkalemia

^a The corrected calcium level in milligrams per deciliter = measured calcium level in milligrams per deciliter + 0.8x (4-albumin in grams per deciliter)

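### Section 6.5.6 permits full-dose restart after any resolved TLS, which Table 3 rules out for treatment-related Grade 4 TLS and, for cemiplimab, modifies for prolonged or recurrent Grade 3 TLS

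*Protocol*

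**What the plan says.** Protocol section 6.5.6 is the event-specific text. It opens with "In case of TLS, study treatment should be held until all serum chemistries have resolved", and on restart it says "TLS complications including renal function should be monitored, and study treatment can be reinstated at full doses after resolution". Table 6 in the same section lists findings that run from laboratory changes alone to seizures, dysrhythmia and heart failure. The section does not separate them by grade, by relationship to treatment, by how long the episode lasted or by whether it is a repeat.

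Protocol section 6.5.3 is the general text. It says that guidance for "hematological and non-hematological adverse reactions in general are outlined in Table 3". The relevant block of that table is headed "Non-hematological toxicity (other than irAE and IAR". Its Grade 4 row reads "Permanent discontinue treatment for treatment related AEs". Its Grade 3 row for cemiplimab, for a first episode over 14 days or a recurrence, says "restart with first reduction dose (Q4W administration if began at Q2W starting dose". The table and its lead-in direct the reader elsewhere for immune-related events and infusion reactions. Neither directs the reader to 6.5.6.

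Two further rules bear on the point. Section 6.5.1 states "Once a dose has been decreased, intra-patient re-escalation back to the previous dose level is not permitted". Section 6.5.2 requires both drugs to be stopped if an interruption exceeds 84 days.

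**The concern.** An investigator with a TLS patient can open either section and find a complete-looking instruction. Where the two differ, the protocol does not say which prevails. The difference is sharpest in the most severe treatment-related case, where one text ends treatment and the other allows it to resume at full dose.

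What is at stake is mainly patient safety and consistent conduct across about 37 planned sites. Any statistical consequence is secondary. The SAP summarizes adverse events leading to definitive or premature discontinuation, dose modification and relative dose intensity, and those entries would depend on which section a site had followed. The point is not purely historical: Protocol section 12.4.5 lets patients stay on study treatment after the final analysis cut-off.

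**Working it through.** No figure in the plan needs reproducing. The check is a row-by-row comparison of restart instructions.

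**Does Table 3 reach TLS?** Its non-hematological block has two exemptions, and TLS is neither. The documents do not formally classify TLS. However, Table 6 defines it by uric acid, potassium, phosphorus, calcium and renal, cardiac or neurological findings, whereas the hematological block of Table 3 deals with blood counts, bleeding and neutropenic infection. The SAP (2.1.4.1 and 2.4.5.2) treats TLS as an adverse event taken from the adverse event forms. Reading TLS as a non-hematological toxicity is therefore natural, but it is an assumption.

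**Row by row:**

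| TLS case | Table 3 | Section 6.5.6 | Result |
|---|---|---|---|
| Grade 2 | Both drugs resume, same dose and schedule | Full doses permitted | Agree on dose |
| Grade 3, first episode under 14 days | Both drugs resume at same dose | Full doses permitted | Agree on dose |
| Grade 3, first episode over 14 days, or recurrence | Isatuximab unchanged; cemiplimab to Q4W if begun at Q2W, or discontinuation considered if begun at DL-1 | Full doses permitted | Differ, cemiplimab only |
| Grade 3, second episode over 14 days, or multiple recurrences | Cemiplimab discontinued | Full doses permitted | Differ, cemiplimab only |
| Grade 4, treatment-related | Permanent discontinuation | Full doses permitted | Incompatible |
| Grade 4, not treatment-related | No discontinuation ordered | Full doses permitted | No direct conflict |

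**Restart threshold.** For Grades 2 and 3, Table 3 waits for Grade 1 or less, or baseline. Section 6.5.6 waits for the chemistries to resolve. A site can satisfy both by waiting for the later of the two, so this is a difference in wording and not a contradiction.

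**Patient already reduced.** In Table 2, cemiplimab is 250 mg in both rows and only the interval changes. Full doses could therefore mean 250 mg per infusion at the current interval, which respects the re-escalation ban. Yet 6.5.3 describes the longer interval as a dose reduction, so full doses could also mean the original Q2W schedule, which would breach the ban. The text supports either reading. The same ambiguity softens the step to Q4W in the third row of the table above, but not the discontinuation in the fourth or fifth row.

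**Time limit.** Section 6.5.2 applies to any interruption for toxicity. Section 6.5.6 does not repeat or mention its 84-day limit. That is an omission, not a contradiction.

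**Who could be affected.** Phase 2 plans 3 × 35 = 105 randomized patients. The 35 in the control arm receive no cemiplimab, so the Grade 3 difference can concern at most 105 − 35 = 70 of them. The Grade 4 conflict can arise in any arm.

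**The case against.** The best defense is that 6.5.6 is the specific rule and Table 3 the general one. Section 6.5.3 presents the table as covering reactions in general and adds "The final decision will be per Investigator's judgment for the best interest of the patient". Section 6.5.6 is headed as guidelines, and its restart wording is permissive. Section 6.5.7 on hepatitis B is another event-specific section that Table 3 does not point to, so a missing pointer alone proves little. There are also safeguards: 6.5.1 lets the investigator stop for any event that warrants it, a restart after more than 14 days needs sponsor consultation, and 84 days is an outer limit.

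Much of this stands, and it lowers the stakes. It does not settle which rule is the default. One section permits what the other rules out, and the protocol never says that the specific text prevails. Section 6.5.1 requires sponsor consultation for modifications that differ from the protocol. With two stated rules, a site cannot tell which course is the departure. The most-conservative rule in 6.5.1 is worded for a patient with several toxicities, not for two rules about one event.

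A reader might go further and infer that 6.5.1 itself orders discontinuation or a reduced schedule for TLS, or that the two texts oppose each other for every TLS. Neither inference is supported. Section 6.5.1 orders neither, and its only friction with 6.5.6 is the re-escalation ban. The comparison also shows agreement on dose for Grade 2 and for a first Grade 3 episode under 14 days, no isatuximab dose difference at Grade 3, and no direct conflict for unrelated Grade 4.

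**Conclusion.** The inconsistency is real but narrow. Section 6.5.6 and Table 3 are incompatible for treatment-related Grade 4 TLS. For cemiplimab only, they also differ for Grade 3 TLS that is prolonged beyond 14 days at the first episode or that recurs. Full doses is ambiguous for a patient already on the reduced cemiplimab schedule, and the 84-day limit is not mentioned in 6.5.6.

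This rests on reading TLS as a non-hematological toxicity, which the text favors but does not state. The Grade 4 conflict does not depend on how full doses is read.

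The size cannot be given. The documents contain no TLS rate and do not assign CTCAE grades to the findings in Table 6. A reader might assume a rate of, say, 1% to 3% and arrive at 0.01 × 105 = 1.05 to 0.03 × 105 = 3.15 patients. That rate is not in the documents, and the sum counts every TLS case, including those where the two texts agree. The number truly caught between the rules would be a subset and may be zero. Nothing in the documents supports a material effect on the response comparison. The reason to act is clarity in a severe treatment-related event.

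**What to change.** Reconcile section 6.5.6 with Table 3, section 6.5.1 and section 6.5.2. State which section governs TLS, put the restart or stop instruction in one place, and have the other refer to it, as Table 3 already does for immune-related events and infusion reactions. Say whether full doses means the amount per infusion or the original schedule, and whether the 84-day limit applies. Which clinical rule is right is for the sponsor's physicians, and this review takes no view on it.

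The cost is a few lines in the next amendment, with no new data, procedures or analyses.
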